Double blind, randomized, sham-controlled trial parallel arm study that will assess the effectiveness and patient perception of the benefit of the Sana Pain Reliever in individuals with chronic pain.

Device:

The Sana Pain Reliever (Sana PR) by Sana Health Inc is a device comprised of one (1) main component (Mask with Earbuds) and two (2) ancillary components (Charger and Headband). The device is worn over the eyes (with earbuds in ears). The device pulses light at a single wavelength but various frequencies throughout a specific firmware algorithm. Through the earbuds, the device also plays different tones in conjunction with the pulses. The device has a skin contacting Heart Rate Variability (HRV) sensor built into the forehead area that measures HRV throughout use.

- Real Arm

Each session with the device will last 15 min and run under the device's normal settings. The session consists of periods of light/sound pulsing at three distinct pulse frequencies; ~8Hz, 3Hz, and 1Hz. For each frequency, there are distinct sections where the audio and visual pulses vary from eye to eye, and ear to ear.

- Sham Arm

Each session with the device will last 15 min and run under the device's sham setting. For the Sham arm, the device will have the light on for 5 min, off for 5 min and then on again for 5 min. Ear plugs will be used in place of headphones. There will be no sound from the device in the sham group.

Application:

The application being used in this study was designed by Sana health specifically for this study. The application controls the Sana Pain Reliever device and allows users to use the device. Users must use the application to start each session with the device, but the device permits multiple, sequential uses of the device without requiring an interaction with the application. The application will be given to participants of this study on a tablet device. Participants will also be given the charging equipment for the device. The application is HIPAA compliant and will undergo InfoSec review at Mount Sinai. Participants will use the application on a tablet device that will be loaned to them for the duration of the study. The application will track data for this study during the at-home portions of the study between the two baseline visits, over the course of the intervention and between the follow-up visits.

- At-home intervention period (week 2 - 10) - tablet and Sana device:

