The application tracks the number of times the device is used in a day and time stamps those sessions. For each session, the application records the HRV data from the forehead sensor of the device and what frequency the auditory and visual stimuli the device emitted during the 15 minutes. Prior to and immediately after each session the application will ask users to rate the amount of pain they are feeling in the moment on a Visual Analog Scale (VAS) along a number line from "no pain" to "worst imaginable pain". The first time the device is used each day, participants will be asked to complete a VAS for how they slept from the night prior. For the last use of the device prior to going to sleep for the day, participants will only be asked to complete the VAS prior to using the device to not disrupt sleep patterns. Additionally, at the last use before sleep participants will be asked to select which of their medication for pain management they took that day. The medications will appear in a drop-down menu on the application. Medications will be reported by each individual to the research team at the first baseline visit week 0 and will be inputted by the research team into each participant's application. Every two weeks during the 8-week intervention period the application will also prompt users to complete the following additional questionnaires: the Neuropathic Pain Symptom Inventory, the Pittsburgh Sleep Quality Index and Patient Health Questionnaire Type 9 for Depression (PHQ-9) and the General Anxiety Disorder 7-item questionnaire (GAD-7). A reminder to complete these biweekly questionnaires will be sent to participant's cell phones via text message and on the tablets themselves. Additionally the application will send compliance messages to participants if participants do not fill out the fortnightly questionnaires.

- Between baseline visits (week 0 – 2) and between follow-up visits (week 10 -14) monitoring of pain at home – tablet only .

During these time periods participants will be asked to use the tablet with the application daily at night prior to sleep. Participants will be asked to complete a VAS of how they slept the night prior, a VAS of pain and asked to report the medications they used that day for pain management.

Description of Procedures Being Performed

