Devices: Participants will be instructed to use the Sana PR every time they experience pain during the day (ad libitum). There will be no minimum or maximum number of uses. Participants will open the Sana Health application and will be prompted to answer the amount of pain they are feeling in the moment using the VAS on the Sana Health application. If it is the first time the participant is using the device for the day, they will also be prompted by the application to complete a VAS to report on how they slept the evening prior. Participants will then turn on the devices using the application. Participants will complete a 15-min cycle with the device. Participants may complete multiple, sequential uses of the device without requiring them to interface with the application. Participants will be prompted to answer the amount of pain they are feeling in the moment after using the VAS on the Sana Health application.

Participants will also be asked to use the Sana PR device every evening immediately prior to/accompanying falling asleep for the night. Participants will open the Sana Health application and will be prompted to answer the amount of pain they are feeling in the moment using the VAS on the Sana Health application. Participants will then be prompted as to what medication they took for their pain that day. The application will be populated with the medications participants reported at the first baseline visit.

Participants will select from this list of medications. Participants will complete a 15 min cycle with the device.

Every two weeks during the 8-week intervention period participants will receive a message on their cellular devices via text message to complete the NPSI, PSQI, PHQ-9 and GAD-7. Participants will be sent compliance reminders to complete these questionnaires on their phones and on the tablet.

Safety monitoring: Participants will be instructed to contact the research team to report any AE over this period. Compliance will be monitored over the 8 week intervention period. A significant decrease in the compliance during (responding to less than 70% of the last 10 scheduled check-ins) of using the device the 8 week intervention will be considered an indication that a participant may need assistance. A research team member will call the participant to ensure that the reason of the drop in usage of the device is not due to an AE.

POST INTERVENTION FOLLOW UP (Week 10) - AT THE ARC OR VIA VIDEO CALL Participant

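### In weeks 2-10 the daily pain, sleep and medication items are described only as steps of a device session, so completeness of the daily record depends on device adherence

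*Combined protocol and SAP*

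**What the plan says.** The Application text in Section 4 (Study Procedures) says the app collects study data "during the at-home portions of the study between the two baseline visits, over the course of the intervention and between the follow-up visits". The items are similar in the three periods, but their triggers differ.

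- **Weeks 0-2 and 10-14.** Each night before sleep, on the tablet and without the device, participants give a sleep VAS, a pain VAS and the pain medication taken that day.
- **Weeks 2-10, daytime.** "Participants will be instructed to use the Sana PR every time they experience pain during the day (ad libitum"), with no lower or upper limit on the number of uses. "Prior to and immediately after each session the application will ask users to rate the amount of pain they are feeling in the moment". The sleep VAS comes with the first device use of the day.
- **Weeks 2-10, bedtime.** "Participants will also be asked to use the Sana PR device every evening immediately prior to/accompanying falling asleep for the night". "For the last use of the device prior to going to sleep for the day, participants will only be asked to complete the VAS" before that session, and the medication item is asked at the same point.

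No step is described for an evening on which the device is not used. The reminders described for weeks 2-10 concern the two-weekly questionnaires: "participants will receive a message on their cellular devices via text message to complete the NPSI, PSQI, PHQ-9 and GAD-7", and "Additionally the application will send compliance messages to participants if participants do not fill out the fortnightly questionnaires". The compliance rule, "responding to less than 70% of the last 10 scheduled check-ins", does not define a check-in and is worded in terms of device use.

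Section 5 plans a mixed model on reported chronic pain and ANOVAs on the outcomes, including pain scores, sleep scores and medication usage. It does not name the pain instrument or say which VAS ratings enter an analysis.

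**The concern.** A daily series that is compared across baseline, treatment and follow-up should be collected in the same way in each. Here the treatment-period record exists only when the device is used. That makes device adherence a condition for observing the outcome, and adherence may be related to that night's pain or may differ between the real and sham arms. A nightly rating that was not taken cannot be collected later.

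There is also a gap in the analysis text. Weeks 2-10 produce three kinds of pain rating: before a pain-triggered session, after a session, and at bedtime before the session. Only the last matches the nightly rating of the other two periods, and Section 5 does not say that comparisons across periods are confined to it.

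**Working it through.** The plan gives no figure to reproduce on this point. The inputs from the plan are the enrolment goal of 180 (Section 4, Subjects) and the schedule. Everything else below is an assumption.

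**Exposure.** Home monitoring covers 14 + 56 + 28 = 98 days, of which 56 (57%), the whole treatment period, use session-tied collection. With all 180 participants followed throughout, there are 180 x 56 = 10,080 treatment-period nights.

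**Nights without a comparable record.** For an assumed bedtime-use rate u, this is (1 - u) x 56 per participant.

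| u | nights per participant | total (x 180) |
|---|---|---|
| 0.9 | 5.6 | 1,008 |
| 0.8 | 11.2 | 2,016 |
| 0.7 | 16.8 | 3,024 |

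These are upper bounds. They include nights when the app would not have been opened at all, which are lost in every period and would still be lost after the fix.

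**Would the compliance rule catch low use?** Assume check-ins are nightly and use is independent between nights. The chance that at least one of the 47 sliding 10-night windows holds fewer than 7 uses is 16%, 74% and 98% at u = 0.9, 0.8 and 0.7.

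**Bias in a bedtime-only analysis.** Assume a 0-10 scale and bedtime pain Normal(5, SD 1.5) in sham and Normal(4, SD 1.5) in real, a true benefit of 1.0. Let P(use) = expit(a + b(pain - 5)), with a set so that sham use equals u. The observed mean in each arm is E[pain x P(use)] / E[P(use)], by numerical integration.

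| b per point | apparent benefit at u = 0.9, 0.8, 0.7 | shift in an arm with mean 5 |
|---|---|---|
| 0.3 | 0.981, 0.968, 0.960 | +0.066, +0.131, +0.194 |
| 0.6 | 0.929, 0.892, 0.869 | +0.125, +0.240, +0.351 |
| -0.3 | 0.985, 0.973, 0.964 | -0.066, -0.131, -0.194 |
| -0.6 | 0.951, 0.917, 0.891 | -0.125, -0.240, -0.351 |

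With b = 0 there is no bias. For b = 0.3 to 0.6 the apparent benefit is 0.93-0.99 with SD 1.0 and 0.81-0.97 with SD 2.0.

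**No true effect, unequal use.** Take 90% use in real and 70% in sham, for reasons other than pain. The spurious difference is the sham shift minus the real shift: 0.194 - 0.066 = 0.128 for b = 0.3, and 0.351 - 0.125 = 0.226 for b = 0.6. It favours the real arm if use rises with pain and the sham arm if use falls with pain.

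**Hypothetical only: all ratings pooled.** The plan does not propose this. With k sessions a day, each rated before and after, plus one bedtime rating, equal use in both arms, identical bedtime pain and a post-session drop 1 point larger in one arm, the pooled contrast is k/(2k + 1): 0.33, 0.40 and 0.43 for k = 1, 2, 3. With equal use and an equal drop, pooling cancels between arms.

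**The case against.** The strongest reply is that the plan already requests the nightly record. Bedtime use is asked for every evening, and the pain rating and medication item come before the cycle runs. This stands, and it narrows the point to nights when the device is skipped but the participant would still have answered. No catch-up for a missed night is described in weeks 0-2 or 10-14 either, so only the additional loss is attributable to the session-tied design, and its share is unknown.

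The check-ins in the compliance rule could be a prompt independent of the device. The documents neither describe nor rule out such a prompt, and the app's behaviour here is inferred from the written procedure. The resulting call may detect low use, but it asks about adverse events and does not restore earlier nights.

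The bias figures stack assumptions. Because bedtime use is requested regardless of pain, the text does not establish pain-dependent use. The shift in an unchanged arm, read as change from baseline, also assumes complete weeks 0-2; similar missingness there would offset it. All of this stands, so the figures show sensitivity and are not predictions.

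A reader might infer that daytime and post-session ratings will be averaged with bedtime ratings. The plan neither proposes nor excludes this. Sessions are time-stamped and bedtime use has its own prompt pattern, so bedtime ratings appear separable at analysis. That part needs a sentence in Section 5, not a design change.

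**Conclusion.** The point holds in a limited form. As written, completeness of the daily pain, sleep and medication series in the treatment period depends on device use, while in the periods before and after it does not. Under the assumptions above, the consequence for a bedtime-only VAS comparison is modest attenuation of a real benefit, or a spurious arm difference of a few tenths of a point at most if use is both pain-dependent and unequal by arm. It is zero if skipped nights are unrelated to pain.

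Two stronger readings are not supported. A reader might infer that weeks 2-10 contain no comparable rating at all; the requested bedtime session supplies one for pain and medication. A reader might also infer that the primary analysis is biased. Section 5 does not name its pain instrument, and the list of data to be collected names the NPSI but no VAS, so an effect is possible but not shown. The NPSI and PSQI, collected every two weeks and at visits, and the medication changes recorded at visits do not depend on sessions. The change is worth making because it is cheap and because missing nights cannot be recovered. Confidence is moderate, since the app's actual behaviour is not documented.

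**What to change.** Have the app ask the bedtime pain VAS and medication items every night in weeks 2-10, before any bedtime session and whether or not the device is used. Device-use instructions stay as they are. Define the check-ins in the compliance rule and say whether they are independent of device use.

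In Section 5, state that VAS comparisons across periods use only this bedtime rating, and that ratings before and after sessions are reported separately as the acute within-session effect.

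If the app cannot be changed, keep the restriction to bedtime ratings, report missing nights by arm, and add a sensitivity analysis for pain-dependent missingness.

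The cost is a prompt change, two or three sentences of text, and one short extra prompt on nights without the device, similar to what participants already answer in weeks 0-2 and 10-14. Aligning the time of the sleep VAS across periods is optional: moving it to bedtime would match the other periods but lengthen recall in weeks 2-10.

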Informed Consent: Participants who fulfill the inclusion/exclusion criteria will be consented to the study at the Abilities Research Center at the start of their first in-person study visit or remotely via a telephone call to talk through the consent form followed by completion of the E-Consent process ahead of their first teleconferenced study visit.

Study devices (mask and tablet) will be shipped together ahead of the first visit for those not completing in-person visits. They will be activated and deactivated remotely at the appropriate times. Those completing study visits in person will receive and return their devices at different stages of the trial (described below).

INITIAL BASELINE CLINICAL ASSESSMENT (Week 0) - AT THE ARC OR VIA VIDEO CALL

Screening: After consent has been obtained participants will complete the Beck Depression Inventory (BDI) at the initial baseline visit. Individuals who score greater than 30 pts on the scale (Severe or Extreme Depression) will be withdrawn from the study.

Participant Information will be collected including:

- Age, gender, name and contact information (phone number(s) and email address).
- Current medications: the list of medications will be collected to add to each participant's Sana Health application.
- A self-reported medical history
- Documentation of the location of their pain on a body chart
- Documentation of what pain management techniques participants typically use

Participants will then complete the following questionnaires:

- Neuropathic Pain Symptom Inventory (NPSI)
- Pittsburgh Sleep Quality Index (PSQI)
- Beck Depression Inventory (BDI)
- Patient health Questionnaire Type 9 for Depression (PHQ-9)
- General Anxiety Disorder 7-item questionnaire (GAD-7)
- World Health Organization Quality of Life BREF (WHOQOL-BREF) & World Health Organization Quality of Life Pain (WHOQOL-pain)

Study Devices: Participants will be loaned a tablet device with the Sana application installed. Participants will be instructed on how to use the device and application.

BASELINE PAIN MONITORING (Week 0 - 2) - AT THE HOMES OF THE PARTICIPANTS

Participants will be asked to use the study tablet with the Sana application daily, at night prior to going to sleep. Participants will be asked to complete a Visual Analog Scale (VAS) of how they slept the night prior, a VAS of their amount of pain and asked to report the medications and strategies they used that day for pain management.

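### In weeks 2-10 the nightly medication log offers only drugs reported at week 0, so as written it cannot record a pain drug started later, although change in medication usage is analysed

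*Combined protocol and SAP*

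**What the plan says.** The rule for weeks 2-10 appears twice in section 4, Study Procedures.

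- **Application description, at-home intervention period.** The question is put once a day: "at the last use before sleep participants will be asked to select which of their medication for pain management they took that day". The response format is given as "The medications will appear in a drop-down menu on the application", and the origin of the entries as "Medications will be reported by each individual to the research team at the first baseline visit week 0". The research team then enters them.
- **INTERVENTION (Week 2 - 10).** "The application will be populated with the medications participants reported at the first baseline visit", followed by "Participants will select from this list of medications".

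The week 0 assessment agrees. It says of the current-medication item that "the list of medications will be collected to add to each participant's Sana Health application".

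Changes in medication are recorded separately at the visits in weeks 2, 10 and 14. Those items do not say that the record is passed to the application. The inclusion criteria require stable medication only for the 4 weeks before week 0. Section 5, Data Analysis plan, includes medication usage among the outcomes assessed for change by ANOVA or a non-parametric equivalent. It gives no definition, unit or data source.

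**The concern.** A daily log is the natural source for a medication outcome in a pain trial, because it shows how often drugs were taken while the device was in use. A list fixed at week 0 makes that log one-sided. It can show a listed drug being taken on more or fewer days, but it cannot show a drug that was not on the list. The clearest case is substitution: a participant who stops a listed drug and starts another appears in the log to have cut down.

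What is at stake is the medication usage result in section 5. If it is taken from the log, new drug use is under-recorded and some substitutions are counted as reductions. A reader could then take a fall in logged use as evidence of reduced need for pain medication.

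**Working it through.** The plan states no figure on this point to reproduce. The check compares the relevant texts and then applies the visit schedule.

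**1. Which record feeds the list?** Only the week 0 report is said to be entered into the application; the application description, the week 0 assessment and the INTERVENTION section agree on this. The change records at weeks 2, 10 and 14 carry no such statement.

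**2. Is there another way into the daily log?** None is described: no free-text entry, no entry for other drugs and no later update. The 48-hour call after the first session is described as covering adverse events, device difficulties and questions. The low-compliance call is to check that a drop in use is not due to an adverse event. Neither is said to collect medication.

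**3. How old is the list?**
- At the start of the intervention: week 0 to week 2 = 2 x 7 = 14 days.
- At its end: week 0 to week 10 = 10 x 7 = 70 days.
- Evenings on which it is used: 8 x 7 = 56.

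**4. What happens to a new drug?**
- Started in weeks 0-2 and noted at the week 2 visit: known to the team, but absent from the list on 56 of 56 evenings.
- Started in weeks 2-10: absent from its start date onward. The next scheduled medication record is the week 10 visit, up to 56 days later.

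**5. What would the log show?** Take, purely as an illustration, a participant who takes one listed pain drug daily, replaces it at week 2 with an unlisted drug taken daily, and answers every evening.
- True days with any pain drug: 56 of 56, or 7 per week.
- Days the log can show: 0 of 56, or 0 per week.

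If the new drug is instead added to the listed one, the log shows 56 of 56 days on the listed drug and no change at all. So substitution appears as a reduction and addition disappears. In the other direction, stopping a listed drug is visible.

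**6. What about amounts?** The question asks which drugs were taken. No dose or count field is mentioned, but no form or application specification is among the documents. Whether doses are recorded is therefore unspecified.

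**The case against.** The strongest reply is that the trial does not lose the added drug. Changes in medication are recorded at three visits after week 0, and section 5 does not say that medication usage comes from the nightly log. If it comes from the visit records, the gap in the log does not reach the analysed outcome. This stands in part. The visit records can show that a drug was added, but they are not described as daily records, and for weeks 2-10 there is one such record, made at the end. Because the source is not named, neither the reader nor the analyst can tell which record counts.

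Four stronger readings are tempting, but the documents do not support them.

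- **That extra doses cannot be recorded.** This would be inferred from silence. The closed list is explicit; the absence of a dose field is not.
- **That the arms are compared with bias.** Both arms use the same log. Bias needs a difference between arms in how often drugs are added or switched, and no rate is given for either arm.
- **That the pain result is distorted.** An unrecorded co-treatment could affect it, but nothing in the documents shows that it does.
- **That the compliance rule shows how many evenings go unrecorded.** The rule ("responding to less than 70% of the last 10 scheduled check-ins") leaves the check-ins undefined and only prompts a telephone call, so it sets no limit on missing entries. Participants are in any case asked to use the device every evening: "Participants will also be asked to use the Sana PR device every evening immediately prior to/accompanying falling asleep for the night".

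It is also fair to object that more tablet work at bedtime sits awkwardly with the plan's wish to protect sleep, which is a secondary outcome. That bears on the design of the fix.

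**Conclusion.** The point holds for the daily log in weeks 2-10, as the documents describe it. A drug started after week 0 cannot be entered, and one already known to the team at week 2 is missing on all 56 intervention evenings. This follows from a stated rule and is more than a missing detail. The second half of the point is that medication usage has neither a definition nor a named source.

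The size of any error in the medication result cannot be estimated, because the documents give no rate of added or switched drugs. The 14, 56 and 70 days describe the schedule, not an error in a result. Medication usage is not among the primary or secondary objectives in section 2, so this is a low-priority improvement.

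The conclusion assumes that the application works as described. If it already has an entry for other drugs, or if staff update the lists, a clarifying sentence would settle that part, and the definition of the outcome would remain to be written. For weeks 0-2 and 10-14 the documents do not restate the response format, so nothing is concluded about those periods.

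**What to change.** - Add *other (name)* and *none today* to the nightly medication prompt. The second option separates an evening without pain medication from an evening without an answer.
- Refresh each participant's list from the changes recorded at the week 2 and week 10 visits.
- Define medication usage in section 5, for example as days per week with any pain drug, listed or added. Name the nightly log as the source and the visit records as a check.
- Report newly started pain drugs by arm. Days with any drug would not reveal a drug added to one already taken daily, so this needs its own line.
- State whether the number of doses is recorded. Collecting it is optional.

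The cost is a small application change, staff time to refresh lists and code free-text names, and slightly more tablet use at bedtime. In the INTERVENTION section the medication question already comes before the evening session. Keeping the new options there means that nothing is added after the last use before sleep, where the plan already omits the pain rating to avoid disturbing sleep. No extra visit is needed.
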